### **3.4 Exploratory Endpoints**

#### **Both Study Cohorts:**

- Association of 1-yr OS with: tumor tissue biomarkers including mutation burden, neoantigen load, immune marker expression [e.g. PD-L1, lymphocyte activation gene 3 (LAG3), indoleamine-2,3-

CONFIDENTIAL

This material is the property of the NYU School of Medicine. Do not disclose or use except as authorized in writing by the study sponsor

dioxygenase (IDO) and T-cell immunoglobulin and mucin domain 3 (TIM3)], and PD-1+ tumor infiltrating lymphocytes (TILs).

- Association of 1-yr OS with baseline and change at 6 weeks in levels of circulating biomarkers, including: regulatory T cells ( $T_{reg}$ ); myeloid-derived suppressor cells (MDSC); and immune cell populations as profiled by high-parameter flow cytometry that simultaneously quantifies expression of proteins related to checkpoint inhibitors (PD1, CTLA4, TIM3, TIGIT, 41BB, CD150, LAG3, BTLA), differentiation status (CD45RA, CCR7, CD57, CD95, CD127), and other traits (CD25, IL12R, CXCR3, CXCR6).
- Effect of study regimen on total lymphocyte counts (TLC) and CD4 counts at fixed timepoints for up to 1 year compared to baseline.
- Explore whether sodium MRI, a non-invasive surrogate measure of cell death in tissue, can differentiate between treatment-related cell death/necrosis ("pseudoprogression") versus tumor progression and serve as a potential non-invasive pharmacodynamic biomarker.

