### 6.1.3 Surgical Study Cohort

The Surgical Study Cohort will open, once the Safety Lead-In in the Main Study Cohort is completed. We will use a single-stage design and enroll a total of 16 patients

After all screening, registration and baseline procedures have been completed as detailed on the **Schedule of Events (Appendix 1)**, subjects will begin study treatment as below:

CONFIDENTIAL

This material is the property of the NYU School of Medicine. Do not disclose or use except as authorized in writing by the study sponsor

On C1D-29, all subjects will initiate study treatment with one dose of nivolumab IV (3 mg/kg) followed by one dose of ipilimumab IV (1 mg/kg).

On C1D-15, all subjects in this cohort will undergo craniotomy and tumor re-resection.

On C1D1, all subjects will receive nivolumab IV (3 mg/kg)

On C1D8, all subjects will begin radiotherapy (RT) to a total dose of 45 Gy, given in 15 consecutive fractions of 3 Gy each fraction.

On C1D15, subjects will receive nivolumab 3 mg/kg and ipilimumab 1 mg/kg IV. Thereafter, nivolumab administration will continue once every 2 weeks and ipilimumab administration will continue once every 6 weeks.

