### 6.5.1 Cycle 1, Day -29 (C1D-29)

After screening and registration procedures, the subject will have all of the C1D-29 Safety Procedures detailed below performed prior to initiating study treatment (first dose of nivolumab and ipilimumab), within

CONFIDENTIAL

This material is the property of the NYU School of Medicine. Do not disclose or use except as authorized in writing by the study sponsor

3 days (except MRI procedures, which can be performed within 21 days) of treatment initiation. Evaluations performed at screening that fall within 3 days of treatment initiation will not need to be repeated. The baseline labs do not need to re-meet the specific eligibility criteria, only meet criteria for dosing.

- Adverse event assessment
- Concomitant medication collection
- Complete physical exam, including neurological exam, and KPS assessment
- Vital signs: When scheduled at the same visit as other procedures, vital signs should be measured prior to clinical laboratory assessments or research blood sample collection.
  - Weight (can be taken within 3 days of scheduled study drug administration), temperature, resting blood pressure, pulse and respiration rate.
  - For C1D-29, the following vital signs will be collected prior to treatment, at the end of the infusions, and every 30 minutes for the first hour post-infusion (all time points  $\pm 10$  minutes):
    - Temperature, resting blood pressure, pulse and respiration rate
- Serum chemistry: sodium, potassium, chloride, bicarbonate, calcium, magnesium, phosphorous, glucose, albumin, creatinine, blood urea nitrogen (BUN), uric acid, ALT, AST, total bilirubin, direct and/or indirect bilirubin, alkaline phosphatase (ALP), lactate dehydrogenase (LDH), amylase, and lipase.
- Hematology: WBC count, 3-cell differential (ANC, monocyte count, lymphocyte count), hemoglobin, hematocrit, platelet count
- T cell subsets (CD3, CD4, and CD8 counts)
- Thyroid stimulating hormone (TSH), free T4
- Pregnancy test (urine or serum  $\beta$ -HCG) for women of child-bearing potential
- Contrast-enhanced brain MRI (within 21 days of study drug initiation)
- Research MRI (sodium MRI) within 21 days of study drug initiation.

Research blood samples. All subjects will have the below research blood samples collected.  
Note: Research blood samples will be taken at 3 time points: **Cycle 1, Day -29 (pre-dose)**, **Cycle 1, Day -15 (surgery)** and **Cycle 1, Day 15** (end of week 6).

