### 6.5.2 Cycle 1, Day -15 (C1D-15)

All patients in the Surgical study cohort will undergo **craniotomy and tumor re-resection** at least 1 week after and within **2 weeks** from first dose of ipilimumab and nivolumab. The following study procedures will be performed:

- Adverse event assessment
- Concomitant medication collection
- Symptom-directed physical exam as clinically indicated by the investigator or qualified designee at all mid-cycle visits
- Vital signs: When scheduled at the same visit as other procedures, vital signs should be measured prior to clinical laboratory assessments or research blood sample collection.
  - Weight (can be taken within 3 days of scheduled study drug administration)
  - Temperature, resting blood pressure, pulse and respiration rate.
- Serum chemistry: sodium, potassium, chloride, bicarbonate, calcium, magnesium, phosphorous, glucose, albumin, creatinine, blood urea nitrogen (BUN), uric acid, ALT, AST, total bilirubin, direct and/or indirect bilirubin, alkaline phosphatase (ALP), lactate dehydrogenase (LDH), amylase, and lipase.
- Hematology: WBC count, 3-cell differential (ANC, monocyte count, lymphocyte count), hemoglobin, hematocrit, and platelet count
- Urinalysis: glucose, blood, pH, specific gravity, ketones, and urine protein
- During the surgery, a tumor specimen will be collected for research studies:
  - Assessment of tumor tissue biomarkers including mutation burden, neoantigen load, immune marker expression [e.g. PD-L1, lymphocyte activation gene 3 (LAG3), indoleamine-2,3dioxygenase (IDO) and T-cell immunoglobulin and mucin domain 3 (TIM3)], and PD-1+ tumor infiltrating lymphocytes (TILs).
- Research blood samples. All subjects will have the below research blood samples collected at time of surgery. Note: Research blood samples will be taken at 3 time points: **Cycle 1, Day -29 (pre-dose)**, **Cycle 1, Day -15 (surgery)** and **Cycle 1, Day 15** (end of week 6). The blood on the surgical date may be taken before or after the surgical procedure.

A total of 40 mL (four 10 mL purple top EDTA tubes) of whole blood will be drawn and immediately sent to the below sites:

- One (1) 10 mL tube will be sent to the Center for Biospecimen Research and Development (CBRD) at NYU School of Medicine (NYU SoM) for acquisition of whole blood, buffy coat, and plasma samples.
- Three (3) 10 mL tubes will be sent to the Immune Monitoring Core (IMC) at NYU SoM and immediately processed for isolation of PBMCs.

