### 6.11.2 Required Research Blood Samples

Research blood samples will be taken at only 2 time points:

**Main Study Cohort: Pre-dose C1D1** (up to 3 days prior to C1D1) and at the **C2D1 visit (end of week 6)**.

**Surgical Study Cohort: Pre-dose C1D-29** (up to 3 days prior to C1D-29) and at the **C1D15 visit (end of week 6)**.

All subjects will have the below research blood samples collected. For details on the timing of specimen collection, refer to the study procedures.

Whole blood for research will be collected from all subjects as described below:

- **NYUSoM subjects:** A total of 40 mL (four 10 mL purple top EDTA tubes) of whole blood will be drawn and immediately sent to the below sites:
  - One (1) 10 mL tube will be sent to the CBRD at NYUSoM for acquisition of whole blood, buffy coat, and plasma samples.
  - Three (3) 10 mL tubes will be sent to the IMC at NYUSoM and immediately processed for isolation of PBMCs.

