26. Ipilimumab will be administered every 6 weeks ( $\pm$ 5 days of scheduled visit) in an outpatient setting as an IV infusion. The ipilimumab dose will depend on individual body weight. The dose of ipilimumab must be adjusted each dose for changes in body weight of  $\geq$ 10%. Dose adjustments for changes in body weight of <10% will be at the discretion of the investigator. Ipilimumab administration will continue for all subjects for 2 years (96 weeks) or until disease progression, intolerable toxicity, death, or the subject meets another withdrawal criterion per protocol.
27. Contrast-enhanced brain MRI: A contrast-enhanced MRI must be obtained within 21 days of the first dose of study treatment. For the Surgical Study Cohort, a post-operative MRI brain must be obtained within 72 hours from craniotomy and tumor re-resection on C1D-15. For response assessment, a contrast-enhanced brain MRI will be performed 8 weeks after study drug initiation, and then every 8 weeks thereafter. MRIs can be performed within 7 days ( $\pm$ 7 days) of scheduled assessment. On-study imaging should follow calendar days (every 8 weeks) and should not be adjusted for delays in cycle starts. Local reading (investigator assessment) will be used to determine eligibility and for participant management. Response Assessments will be performed on every brain imaging assessment performed on protocol per RANO criteria, although non-traditional iRANO criteria may be used for patient management (see **Appendix 3**).

CONFIDENTIAL

This material is the property of the NYU School of Medicine. Do not disclose or use except as authorized in writing by the study sponsor

28. Research Blood Samples: For all patients, whole blood will be drawn at two time points: At pre-dose C1D-29 (-3 days) and at C2D15(±/- 3 days). Four purple top EDTA tubes (40 mL) will be drawn, one EDTA tube will be sent to the CBRD and three EDTA tubes will be sent immediately to the IMC.
29. Research (sodium) MRI: All subjects must have a research MRI performed prior to C1D1 (within 7 days of study drug initiation) and at every response assessment time point on study treatment (i.e., every 8 weeks after study drug initiation, and then every 8 weeks thereafter). Research MRIs can be performed within 7 days (±7 days) of scheduled assessment. Research MRIs must be performed at NYUSoM.

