34. Survival follow up: Following the 90-day post-drug visit, all subjects will be contacted every 3 months (±14 days) to assess for study-treatment related toxicities, initiation of any new anti-cancer treatments, and survival status. Contact may be performed by a site visit, telephone contact, e-mail, or mail. The date of death, initiation of any new anti-cancer treatments and date of last contact should be documented if this information is available. All subjects will be followed post-treatment until death, withdrawal of permission to record at least survival data, or subject is lost to follow-up. If a subject withdraws permission to record at least survival data after coming off treatment, this must be documented along with the date the subject withdraws permission as per details in Section 6.12. All reasonable efforts must be made to locate subjects to determine and report their ongoing status. Lost to follow-up is defined by the inability to reach the subject (or the subject's next-of-kin if the subject does not respond) after a minimum of two documented phone calls, faxes, or emails in a 3 month period over two consecutive 3 month periods, a lack of response by subject to one registered mail letter, and if no medical records are available to be reviewed (See study procedures for details).
35. T cell subsets (CD3, CD4, and CD8) will be collected at the following 5 time points only: baseline (pre-C1D1), C2D1, C4D1, C6D1, and C8D1.
36. After informed consent, if subjects undergo tumor resections or biopsies prior to treatment initiation, during the study period, or after progression on study drug, a small amount fresh surgical specimen (approximately 0.5 cm^2, approximately equivalent to amount required for a stereotactic needle biopsy) will be collected for shortterm (6-8 days) patient-derived organotypic tumor spheroid (PDOTS) culture and for dissociation into single cell suspensions for flow-cytometry-based immunoprofiling. Tumor sample will be collected in medium (DMEM) in a sterile cryotube and immediately transported on ice to [name] laboratory at NYU Langone for immediate processing.

CONFIDENTIAL

This material is the property of the NYU School of Medicine. Do not disclose or use except as authorized in writing by the study sponsor

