#### **3. Research Blood Samples**

Research blood samples will be taken at only **2 timepoints**: Baseline (prior to Cycle 1, Day 1) and at Cycle 2, Day 1 (Week 6), as per the study procedures (Section 6) and the Schedule of Events, Appendix 1.

Research blood samples will be collected from all subjects as detailed below:

- 40 mL (four 10 mL purple top EDTA tubes) of whole blood will be drawn and immediately sent to the below sites:
  - One (1) 10 mL tube will be sent to the Center for Biospecimen Research and Development (CBRD) at NYUSoM for acquisition of whole blood, buffy coat, and plasma samples.
  - Three (3) 10 mL tubes will be sent to the Immune Monitoring Core (IMC) at NYUSoM and immediately processed for isolation of PBMCs.

CONFIDENTIAL

This material is the property of the NYU School of Medicine. Do not disclose or use except as authorized in writing by the study sponsor

All blood samples from non-NYUSoM sites should be sent to the CBRD at NYUSoM at the address below. Research blood specimens collected from NYUSoM subjects will be transported immediately to either the CBRD or the IMC (address below) as described above.

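### For the surgical cohort, Appendix 2 footnotes 28 and 35 and Appendix 7 give blood-sampling visits that contradict Section 6.5 and the Appendix 2 grid and, for research blood, miss week 6

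*Combined protocol and SAP*

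**What the plan says.** Section 6.1.3 sets the start of treatment for the surgical cohort: "On C1D-29, all subjects will initiate study treatment with one dose of nivolumab IV (3 mg/kg"), followed by ipilimumab. Re-resection is at C1D-15, and C1D1 is the second nivolumab visit.

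For research blood in this cohort:

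- Section 6.5.1 says "Research blood samples will be taken at 3 time points" and names C1D-29 pre-dose, C1D-15 at surgery, and C1D15. Sections 6.5.2 and 6.5.5 repeat this, and the Appendix 2 grid marks the same three visits.
- Section 6.11.2 says "Research blood samples will be taken at only 2 time points" and, for this cohort, names C1D-29 pre-dose and C1D15, described as the end of week 6.
- Appendix 2, footnote 28, says "whole blood will be drawn at two time points: At pre-dose C1D-29 (-3 days) and at C2D15".
- Appendix 7, item A.3, gives "Baseline (prior to Cycle 1, Day 1) and at Cycle 2, Day 1 (Week 6") without separating the cohorts. Its sections on peripheral blood flow cytometry and deep sequencing give baseline and C2D1 for all subjects, and its TCR section names C2D1 as the post-treatment sample.

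For CD3, CD4 and CD8 counts, Appendix 2 footnote 35 allows five time points only: "baseline (pre-C1D1), C2D1, C4D1, C6D1, and C8D1". The main-cohort footnote 35 in Appendix 1 gives the same list.

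Section 3.4 lists, for both cohorts, "Association of 1-yr OS with baseline and change at 6 weeks in levels of circulating biomarkers", and separately lymphocyte and CD4 counts at fixed time points for up to a year against baseline. Section 7.2.4 plans signed-rank tests on paired changes and logistic regression of 1-year survival on baseline levels and changes.

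**The concern.** The main and surgical cohorts use the same cycle-day labels with different origins. In the main cohort the first dose is C1D1 and C2D1 is week 6. In the surgical cohort dosing starts before C1D1, so a visit name carried across from the main cohort points to a different time on treatment. The footnotes to the surgical schedule and the biomarker appendix name visits that are not week 6 in this cohort, and a site coordinator works from exactly those lines.

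At stake is the week-6 sample. By C2D15 a patient has also had the C1D15 infusions of both drugs, nivolumab at C1D29 and C2D1, and the rest of a radiotherapy course that began at C1D8. A week-12 sample therefore cannot stand in for a week-6 one. A change variable that mixed weeks 6, 10 and 12 would confuse time and exposure with the biomarker effect, and a draw that was not taken cannot be recovered.

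**Working it through.** **Inputs.** First dose at C1D-29 (Section 6.1.3). Surgery nominally 14 days later (Section 3.1.3), permitted from 7 to 14 days (Section 6.5.2). C1D1 is 14 days ±3 after surgery (Section 6.5.3). A cycle is 42 days (Section 6.5). Visit window ±3 days (Sections 6.5.5, 6.5.7 and 6.5.8).

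**The plan's own figure.** C1D1 = 14 + 14 = day 28 after first dose. C1D15 = 28 + 14 = day 42 = week 6. This reproduces the label in Section 6.11.2.

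**The other visits.** C2D1 = 28 + 42 = day 70 = week 10. C2D15 = 28 + 42 + 14 = day 84 = week 12, twice the intended interval. Counting the day labels literally, with or without a day 0, adds one or two days (43–44, 71–72 and 85–86) and changes nothing.

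**With the windows.** C1D1 falls between 7 + 11 = day 18 and 14 + 17 = day 31. Each later visit runs from 18 + offset − 3 to 31 + offset + 3.

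| Visit | Offset from C1D1 | Nominal day | Range | Contains day 42? | Named as the on-treatment research draw by |
|---|---|---|---|---|---|
| C1D15 | 14 | 42 | 29–48 | yes | 6.5.1, 6.5.2, 6.5.5, 6.11.2, Appendix 2 grid |
| C2D1 | 42 | 70 | 57–76 | no | Appendix 7 |
| C2D15 | 56 | 84 | 71–90 | no | Appendix 2 footnote 28 |

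In the main cohort C2D1 is 42 days after first dose, so the week-6 label in Appendix 7 is right there and only there.

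**Number of draws.** Three in Sections 6.5.1, 6.5.2 and 6.5.5 and the grid; two in Section 6.11.2, footnote 28 and Appendix 7. The grid has no C2D15 column, so footnote 28 contradicts the row it annotates.

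**T-cell subsets.**

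- Section 6.5.1: C1D-29. Section 6.5.5: C1D15.
- Section 6.5.7: C2D1, C4D1, C6D1 and C8D1 only.
- Section 6.5.8: C2D15, C4D15, C6D15 and C8D15 only.
- Section 6.5.9, a Day 29 visit, carries the Day 1 list.
- Grid: screening, C1D-15, C1D1 and C1D15; nothing at C1D-29 or C2D1.
- Footnote 35: five visits that leave out C1D15, although the footnote marker sits on the C1D15 cell.

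**Literal reading of the footnote 35 baseline.** Assume the 3-day baseline window of footnote 12 applies before C1D1. The draw would then fall 28 − 3 = 25 to 28 days after the first doses of both drugs and 14 − 3 = 11 to 14 days after craniotomy.

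**The case against.** The strongest reply is that the right samples are already specified and the documents largely say where to look. Section 6.5 and the grid provide a pre-dose C1D-29 sample and a C1D15 sample. Sections 6.11 and 6.11.2 refer timing to the study procedures, and item A.3 of Appendix 7 cites Section 6. This stands, and it defeats one inference a reader might draw, that the planned 6-week change cannot be derived. It can, if Section 6.5 is followed. What remains is that footnote 28 and the flow cytometry, TCR and deep sequencing text of Appendix 7 carry no such deferral, and A.3 also cites Appendix 1, the main-cohort schedule.

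A reader might also infer that this cohort has no pre-treatment baseline. The documents do not support that. Footnote 28's own baseline is correctly pre-dose. Footnote 12 ties its pre-C1D1 baseline to the 3 days before first dose, which is the natural reading of footnote 35 too. Section 6.5.1 collects T-cell subsets at C1D-29, and the grid marks them at screening. Only footnote 35 and item A.3, read alone, could put a baseline after dosing and surgery.

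Nor is carry-over from the main cohort the whole explanation. It fits footnote 35 and Appendix 7, but footnote 28's C2D15 is not a main-cohort research draw.

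Section 6.5.2 says "The blood on the surgical date may be taken before or after the surgical procedure". One might want that timing fixed, but no endpoint in Section 3.4 names the surgery-day blood, so that is a separate preference. Likewise, neither Section 3.4 nor Section 7.2.4 says the cohorts will be pooled.

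**Conclusion.** The contradiction is real and would be acted on at the bedside. For the surgical cohort, footnote 28 places the second research draw at about week 12 and Appendix 7 at about week 10. Only C1D15, as in Sections 6.5 and 6.11.2 and the grid, can be the 6-week sample. Staff who follow footnote 28 or Appendix 7 would miss both the week-6 and the surgery-day draws. Staff who follow Section 6.11.2 would miss only the surgery-day draw. Footnote 35's T-cell list conflicts with Sections 6.5.1, 6.5.5 and 6.5.8 and with the grid.

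The reach is limited. At most 16 patients are concerned, and only those whose draws follow the conflicting lines. Section 7.2.4 calls the correlative biomarker endpoints exploratory and hypothesis generating; no primary endpoint of either cohort is touched. The week counts rest on the nominal intervals, but the separation of C1D15 from C2D1 and C2D15 also holds across all the stated windows.

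**What to change.** 1. In Appendix 2 footnote 28 and in Appendix 7 (item A.3 and the TCR diversity, flow cytometry and deep sequencing text), state for the surgical cohort: pre-dose C1D-29, C1D-15 and C1D15 (week 6). Keep pre-dose C1D1 and C2D1 for the main cohort.
2. Bring Section 6.11.2 into line with Section 6.5 so that the number of draws is the same everywhere.
3. In Appendix 2 footnotes 12, 29 and 35, replace the pre-C1D1 label with before first dose (C1D-29). In footnote 29 also reconcile the 7-day sodium MRI window with the 21 days in Section 6.5.1.
4. Settle one list of T-cell subset visits for this cohort and use it in footnote 35, Sections 6.5.1, 6.5.5 and 6.5.7 to 6.5.9, and the grid. The list should include the pre-dose baseline and the later fixed visits that the one-year CD4 endpoint needs.

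The cost is a wording amendment. Section 6.5 and the grid already provide for the three research draws, so no visit or research sample is added. The one decision for the sponsor is the T-cell list, because Section 6.5 and the grid disagree with each other there.

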### 15.3 Appendix 3: Karnofsky Performance Status Scale

Karnofsky Performance Scale	
Percent	Description
100	Normal, no complaints, no evidence of disease.
90	Able to carry on normal activity; minor signs or symptoms of disease.
80	Normal activity with effort; some signs or symptoms of disease.
70	Cares for self, unable to carry on normal activity or to do active work.
60	Requires occasional assistance, but is able to care for most of his/her needs.
50	Requires considerable assistance and frequent medical care.
40	Disabled, requires special care and assistance.
30	Severely disabled, hospitalization indicated. Death not imminent.
20	Very sick, hospitalization indicated. Death not imminent.
10	Moribund, fatal processes progressing rapidly.
0	Dead.

CONFIDENTIAL

This material is the property of the NYU School of Medicine. Do not disclose or use except as authorized in writing by the study sponsor

